## Abbreviations:

AE=Adverse event;

BC=Baseline Cycle;

CCI

C-SSRS=Columbia-Suicide Severity Rating Scale;

CCI

DYS=Dysmenorrhea;

CCI

eDiary=Electronic diary;

EOT=End of Treatment;

ERP=Endometriosis-related pain;

CCI

NRS=Numeric rating scale;

OPP=Overall Pelvic Pain (endometriosis-related);

PD=Pharmacodynamic;

PGI-S=Patient Global Impression of Severity;

PROMIS= Patient Reported Outcomes Measurement Information System;

CCI

 $t_{max}$ =Time taken to reach the maximum concentration

TRC1=Treatment Cycle 1;

TRC3=Treatment Cycle 3;

V=Visit;

AUCtau=Area under the plasma-concentration-time curve during a dosing interval, calculated by linear up/log down trapezoidal summation;

BID=Twice a day;

Cmax=Maximum concentration, obtained directly from the observed concentration versus time data;

CCI

CCI

CCI

ECG=Electrocardiogram;

EHP-30=Endometriosis Health Profile-30;

CCI

CCI

NMPP=Non-menstrual pelvic pain;

CCI

CCI

PGI-C=Patient Global Impression of Change;

PK=Pharmacokinetic;

SC=Screening Cycle;

CCI

CCI

TRC2=Treatment Cycle 2;

CCI

CCI

**Table 2 Estimand and analysis for primary efficacy endpoint**

Primary Efficacy Objective:  To evaluate the efficacy of 3 dose levels of OG-6219 (Group A, B, C) versus Placebo (Group D) in reducing OPP during TRC3, as measured by a NRS in the eDiary	
Estimand:  The mean difference between each OG-6219 dose arm and placebo in change from BC to TRC3 of the mean OPP score, assuming that all participants completed the treatment period.	
Treatment:  OG-6219 CCI BID; OG-6219 CCI BID; OG-6219 CCI BID; placebo BID	
ESTIMAND	ANALYSIS
Target Population	Analysis Set
Pre-menopausal women between 18 and 49 years of age (inclusive) who have moderate to severe ERP and meet all other study inclusion/exclusion criteria	Participants allocated to treatment who took at least one dose of study medication and who completed at least one subsequent diary entry. Corresponds to the MFAS.
Variable	Outcome Measure
Change from BC to TRC3 of the mean OPP score	Change from BC to TRC3 of the mean OPP score  Data after the last day of treatment will not be included in TRC1-TRC3, but only in SFC.
Handling of Intercurrent Events	Handling of Missing Data
Premature treatment discontinuation for any reason, including adverse event or lack of efficacy: a hypothetical strategy will be used, i.e. it will be assumed that treatment discontinuation did not occur and that participants completed the treatment period.  Use of study supplied rescue medication for ERP per the protocol is not considered to be an intercurrent event.  Use of prohibited pain medication is not considered to be an intercurrent event.	MAR (Missing at Random) will be assumed for the primary analysis.
Population-level summary measure	Analysis approach

Mean difference between each OG-6219 dose arm and placebo in change from BC to TRC3 of the mean OPP score.	The mean OPP score will be analyzed using a longitudinal model, i.e. a Mixed Models for Repeated Measures (MMRM), fitted to data from all participants with a post-treatment OPP measurement. The response vector for the model will be change from BC in the mean OPP score during TRC1, TRC2, and TRC3. Model terms will include the Baseline Cycle value (mean OPP score for BC), treatment, time (i.e., cycle), and treatment-by-time interaction. An unstructured error structure will be assumed. If nonconvergence under the UN assumption is encountered a compound symmetry (CS) and autoregressive AR(1) error structures will be assumed in sequence. Estimated treatment differences (each OG-6219 treatment group versus Placebo) with corresponding 95% CI and 2-sided p-values will be derived from the model for each treatment cycle.
--	--

## 4. STUDY DESIGN

### 4.1. Overall Study Design

This is a global multicenter, Phase 2a/b, randomized, double-blind, Placebo-controlled, 4-arm proof of concept, dose-range study to assess the efficacy, safety, and tolerability of 3 dose levels of OG-6219, in pre-menopausal women 18 to 49 years of age (inclusive), who have been surgically diagnosed with endometriosis within the last 4 months to 10 years prior to Visit 1 (V1) and with moderate to severe ERP.

The study duration of approximately 28 weeks includes: an initial period of approximately 2 to 4 weeks between V1 and CCI to collect safety laboratory assessments. Each cycle refers to one menstrual cycle. A Screening Cycle (SC), between CC and CCI. A Baseline Cycle (BC) or Single-blind CCI, between CC and CCI. A Randomization Visit CCI, with treatment allocation CCI to three OG-6219 dosing arms and one Placebo arm. The randomized treatment period consists of three menstrual cycles, Treatment Cycle 1 (TRC1), Treatment Cycle 2 (TRC2), and Treatment Cycle 3 (TRC3), followed by a Safety Follow-up Cycle (SFC). The study includes 9 on-site visits and 9 phone contacts, as detailed below and illustrated in Figure 1:

**Screening Period:**

- SC: Starts at CC (first day of the menses) and ends one-day before next menses.
- BC during the single-blind, CCI period: Starts at CC (first day of the menses) and ends at one-day before next menses.

**Randomization:** CC, this is on first day of the next menses after the end of BC.

**Treatment Period:** Three treatment cycles (TRC1, TRC2, and TRC3) after CC:

- TRC1 is the period between the first day of menses associated with treatment start CCI to the day prior to the first day of next menses, regardless of number of days. CCI
- TRC2 is the period between the first day of second menses after end of BC to the day prior to first day of next menses, regardless of number of days. Phone Contact 1 is done during the menses.
- TRC3 is the period between the first day of third menses after end of BC to either end after C completed cycles or CCI on study treatment, whichever occurs first.

**Safety Follow-up:**

- SFC, is the period of time between the first day after stopping study treatment ending after 30 consecutive days (regardless of whether it aligns with first day of menses or not). Phone contact C is done CCI after last intake of study treatment. Visit C is considered End of Study (EOS).

At CC, participants will receive the eDiary (eCOA) which will be used CCI until the EOS (CC) to CCI collect the (worst) CCI pelvic pain score. The eDiary should be completed at about the same time (before going to bed), within a 24-hour recollection period. The eDiary will also collect CCI

as well

as mental health assessment via C-SSRS will be collected at visits according to the Schedule of Activities (SoA) included in Section 4.4.

**Figure 1: Study Schema (copied from the study protocol)**

CCI

## 4.2. Statistical Hypotheses

The following three hypotheses will be tested for the primary endpoint:

- 1) **H0:** The change in mean OPP score from BC to TRC3 is the same for Group C (CCI [redacted] BID) and Group D (Placebo) vs.  
**H1:** The change in mean OPP score from BC to TRC3 is different for Group C (CCI [redacted] BID) and Group D (Placebo).
- 2) **H0:** The change in mean OPP score from BC to TRC3 is the same for Group B (CCI [redacted] BID) and Group D (Placebo) vs.  
**H1:** The change in mean OPP score from BC to TRC3 is different for Group B (CCI [redacted] BID) and Group D (Placebo).

3) **H0:** The change in mean OPP score from BC to TRC3 is the same for Group A (CCI BID) and Group D (Placebo) vs.

**H1:** The change in mean OPP score from BC to TRC3 is different for Group A (CCI BID) and Group D (Placebo).

The three hypotheses will be tested separately at the 2-sided  $\alpha$  level of 0.05 without any adjustment for multiplicity.

#### 4.3. Sample Size

Approximately 760 pre-menopausal females aged 18 to 49 years old (inclusive), who have been surgically diagnosed with endometriosis within the last 4 months to 10 years prior to V1, will be screened to achieve 380 randomly assigned to the study treatment (95 participants in each group). A total of 380 participants will provide 84% power to detect a difference of 1 point between an OG-6219 dose group and Placebo in change from baseline to TRC3 of mean OPP, assuming a common SD of 2.2. This power calculation is based on a 2-sided test with Type I error of 0.05 and a dropout rate of 10%.

A minimum subset of 10 participants per group (~10%) will be enrolled for optional intensive PK sampling for the entire duration of the study.

#### 4.4. Schedule of Activities

The schedule of activities is shown in the Study Protocol, section 1.3.

## 5. COVARIATES AND SUBGROUPS

### 5.1. Planned Covariates and Factors

The statistical analyses will include treatment, time, and treatment-by-time interaction as factors (if only one timepoint is included in the analysis, treatment will be the only factor). The baseline value of the endpoint will be included as a covariate (for endpoints where a baseline value exists).

### 5.2. Subgroups

Demographic data, baseline characteristics, concomitant medications, and selected safety data will be summarized by region (US vs. Non-US). No specific subgroup analyses are planned, but such may be performed if deemed to be necessary.

## 6. ANALYSIS SETS

### 6.1. Definitions of Analysis Sets and Subgroups

Agreement of participants inclusion/exclusion from each analysis set will be conducted prior to database lock.

Analyses will be performed in the respective analysis sets (efficacy analyses in the MFAS for on-treatment efficacy, SFAS for post-treatment efficacy, selected efficacy analyses in the PP analysis set, safety analyses in the SAF, PK analysis in the PK analysis set and PK analysis Set for NCA, and PD analysis in the PD analysis set). The randomized treatment will be used for the ENR, FAS, MFAS and PP analysis sets. The actual treatment received will be used for the SAF, SFAS, PD, PK, and PKNCA analysis sets. If for any participant the randomized treatment differs from the actual treatment received, the primary efficacy analysis will be repeated using the actual treatment received. If a participant would receive a different treatment than the one randomized to during parts of the treatment period, the actual treatment received for this participant will be defined as the treatment with the longest

exposure time.

## **6.2. All Participants Enrolled Analysis Set [ENR]**

The all participants enrolled analysis set will contain all participants who provided informed consent for the study.

## **6.3. Full Analysis Set [FAS]**

The Full Analysis Set will include all randomized participants.

## **6.4. Modified Full Analysis Set [MFAS]**

The Modified Full Analysis Set (MFAS) is defined as all randomized participants who received at least one dose of study medication and who completed at least one subsequent diary entry for DYS or NMPP.

## **6.5. Per-Protocol Analysis Set (PP)**

The Per-Protocol analysis set is defined as a subset of all participants in the MFAS with the following exclusions.

The PP analysis set will exclude participants that either:

- Had critical or major protocol deviation with major impact on the primary endpoint.
- Were non-compliant with randomized treatment, i.e. used <75% of the protocol dose of randomized study treatment (only participants for which compliance could be calculated from randomization to last dose of treatment, and for which this compliance was <75%, will be excluded).

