9.2 Analysis Sets

- Full Analysis Set (FAS)—all participants randomized
- Modified Full Analysis Set (MFAS)—all participants randomized who receive at least 1 dose of study treatment and who completed at least 1 subsequent diary entry CCI
- Per Protocol (PP)—all participants in the MFAS who completed at least one treatment cycle with no major protocol deviations that may impact the interpretation of the primary efficacy endpoint
- Safety (SAF)—all participants who received at least 1 dose of study treatment
- Safety Follow-up Analysis Set (SFAS)—all participants randomized who receive at least 1 dose of study treatment and have at least 1 diary entry CCI after the date of last treatment
- PK Analysis Set: The PK analysis set is a subset of the Safety analysis set (SAF) and will include all participants who received at least a dose of OG-6219 and have at least 1 quantifiable OG-6219 or FOR-1011 concentration.
- Pharmacokinetic Analysis Set for Noncompartmental Analysis: The PK analysis set for noncompartmental analysis (NCA) will include all participants in the PK analysis set CCI chose intensive PK sampling CCI and have sufficient samples to determine at least one PK parameter for OG-6219 or FOR-1011. Intensive PK sampling is optional where a separate consent would be provided.
- PD Analysis Set—The PD analysis set is a subset of the SAF and will include all participants who received at least a dose of OG-6219 or Placebo and have at least 1 quantifiable PD endpoint without protocol deviations or events affecting the PD results.

Analyses will be performed in the respective analysis populations (safety analyses in the safety set, PK analysis in the PK analysis set and PK analysis Set for NCA, PD analysis in the PD analysis set, and efficacy analyses in the MFAS for on-treatment efficacy, SFAS for post-treatment efficacy, and select efficacy analyses in the FAS and/or PP analysis set).

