9.4.2 Primary Endpoint Analysis

The primary endpoint will be the mean change from BC of the average daily OPP score during TRC3. The OPP will be calculated for each cycle as the total of OPP scores reported during the cycle divided by the number of days during the cycle in which the score was reported. For participants who discontinue early, their last cycle will be associated with the cycle number at entry into the cycle. The primary analysis will be conducted using the MFAS and will use a longitudinal model. The response vector for the model will be change from BC in the average OPP during TRC1, TRC2, and TRC3. Model terms will include the respective baseline, treatment, time (ie, cycle), and treatment-time interaction, allowing for the inclusion of individual outcomes over time (cycle). An unstructured error structure will be assumed. If

nonconvergence is encountered, compound symmetry (CS) and first-order autoregressive AR(1) error structures will be considered.

Least squares mean change from baseline for each treatment group, with corresponding standard errors will be provided. Estimated treatment differences (each active treatment group versus Placebo) with corresponding 95% CI and 2-sided p-values will also be provided for each active treatment group. No missing data will be imputed for the primary analysis.

Supportive analyses will be conducted using an analysis of covariance (ANCOVA) on the change from baseline to the TRC3, with treatment as a fixed factor and baseline OPP as a covariate.

The primary longitudinal and ANCOVA models will be repeated using the PP set.

A completers analysis will be performed for those participants who completed all 3 treatment cycles. Details regarding additional sensitivity and subgroup analyses of the primary efficacy endpoint will be described in the SAP.

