#### 8.2.6.2. STUDY TREATMENT COMPLIANCE

Compliance with the use of study treatment overall will be presented for the SAF. Number of tablets dispensed and number of tablets returned will be taken from the eCRF Drug Accountability form. Non-compliance is defined as compliance to study treatment <75%. Non-compliance to study treatment will be summarized overall using descriptive statistics by treatment group.

Compliance (%) with randomized study treatment will be calculated based on drug accountability data as the total number of tablets taken (total dispensed – total returned) divided by the total expected number of tablets (number of tablets should be taken per day times duration of exposure) expressed as a percentage, see calculation below.

$$100 \times \frac{\sum(\text{\#tablets dispensed} - \text{\#tablets returned})}{\text{\#tablets that should be taken per day} \times \text{duration of exposure}}$$

Where # of tablets that should be taken per day is 6 tablets (1 tablet from Bottle A BID and 2 tablets from Bottle B BID), and duration of exposure (days) = date of last randomized study treatment administration – date of first randomized study treatment administration + 1.

For participants where bottles were not returned or lost, compliance will not be calculated but set to missing.

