### 8.3.7. Supplementary Analyses for Primary Efficacy Endpoint

Two supplementary analyses will be performed for the MFAS, both using analysis of covariance (ANCOVA) models on the change from baseline to TRC3 with treatment as a fixed factor and baseline OPP as a covariate. In the first analysis, only subjects with data from TRC3 will be included. In the second analysis, subjects without data from TRC3 will have their TRC3 value imputed using last observation carried forward (i.e. the last available of the TRC2 and TRC1 values will be used.)

Estimated treatment differences (each OG-6219 treatment group versus Placebo) with corresponding 95% CI and 2-sided p-values will be derived from the model.

Analysis using an ANCOVA model will be implemented using the SAS® procedure MIXED as follows (example code only):

```
PROC MIXED DATA = ...;  
  CLASS TREATMENT;  
  MODEL CHG = BASELINE TREATMENT;  
  LSMEANS TREATMENT / PDIFF CL;  
RUN;
```

where CHG = change from baseline to TRC3

TREATMENT = randomized treatment group (CCI BID, CCI BID, CCI BID, and placebo)

BASELINE = baseline cycle value

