## 10. CHANGES TO PROTOCOL-PLANNED ANALYSES

There were no changes to the analyses planned in the study protocol.

The study protocol did not include a description of the estimand. This has now been included in the SAP.

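### The SAP drops the protocol's one-completed-cycle condition for the PP set, the PP ANCOVA and the completers analysis, while its section 10 reports no changes

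*SAP*

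**What the plan says.** **PP set.** Protocol 9.2 defines it, with reference to the primary efficacy endpoint, as "all participants in the MFAS who completed at least one treatment cycle with no major protocol deviations that may impact the interpretation". SAP 6.5 starts from the MFAS and makes two exclusions. The first covers women who "Had critical or major protocol deviation with major impact on the primary endpoint". The second covers women who took less than 75% of the randomised dose, but it applies to "only participants for which compliance could be calculated from randomization to last dose of treatment". No minimum number of cycles is required.

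**Compliance.** SAP 8.2.6.2 divides tablets taken by 6 per day times the days from first to last dose. It adds: "For participants where bottles were not returned or lost, compliance will not be calculated but set to missing".

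**Analyses.** Protocol 9.4.2 plans to repeat both the longitudinal model and the ANCOVA on the PP set. It also states: "A completers analysis will be performed for those participants who completed all 3 treatment cycles". SAP 8.3.6 repeats only the primary MMRM on the PP set. SAP 8.3.7 runs two ANCOVAs, both in the MFAS. For one of them, "In the first analysis, only subjects with data from TRC3 will be included"; the other carries the last observation forward (LOCF).

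**Disclosure.** SAP 10 states: "There were no changes to the analyses planned in the study protocol". It mentions only that the estimand was added.

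**The concern.** A PP analysis is read as the result in women treated broadly as planned, and a completers analysis as the result in women who finished treatment. The primary estimand is hypothetical: it takes every woman to have completed treatment and relies on a missing-at-random assumption (SAP Table 2 and 8.1.6). These two supportive analyses are where a reader would look for the result in women who actually received the planned treatment. The same PP set also serves the DYS, NMPP and dyspareunia endpoints (SAP 8.4.3).

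If the set's definition changes and a planned analysis disappears without being listed, the study report can present a PP result that differs from the one the protocol describes. A reader who relies on SAP 10 would not know.

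**Working it through.** **1. The plan's own figure.** Inputs from SAP 4.3: 95 per arm, 10% dropout, difference 1 point, SD 2.2, two-sided 0.05.

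- Evaluable per arm: 95 × 0.90 = 85.5.
- Standard error of the difference: 2.2 × √(2/85.5) = 0.3365.
- Power: Φ(1/0.3365 − 1.96) = 0.844.

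The stated 84% is reproduced. It concerns the primary analysis and does not depend on how the PP set is defined.

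**2. The two documents side by side.**

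| Item | Protocol 9.2 / 9.4.2 | SAP 6.5 / 8.3.6 / 8.3.7 |
|---|---|---|
| At least one cycle completed | Required for PP | Absent |
| Compliance below 75% | Not a PP criterion | New exclusion |
| MMRM on PP | Planned | Planned |
| ANCOVA on PP | Planned | Absent |
| Completers of all 3 cycles | Planned | Absent |

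Both columns come from the current text, and the SAP says it is based on protocol version 6.0.

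**3. Can the compliance rule replace the cycle condition?** Compliance = 100 × tablets taken / (6 × days from first to last dose).

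- A woman who takes every tablet and stops after 4 days scores 100 × 24/(6 × 4) = 100%.
- Three cycles of 21 to 32 days would be 63 to 96 days, or 378 to 576 tablets. She has taken 24/576 to 24/378 of that, about 4–6%.
- If she does not return her bottles, her compliance is missing and she is not excluded.

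Stopping early therefore cannot lower the measure.

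**4. Does she reach the PP model?** One dose and one later diary entry put her in the MFAS (SAP 6.4). One score is enough for a cycle mean (SAP 8.3.3). She is in the PP MMRM unless the deviation criterion removes her.

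**5. How many women?** Dropouts: 0.10 × 380 = 38. The documents give no timing of dropout, so the share stopping in TRC1 is an assumption.

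| Share of dropouts in TRC1 | Women | % of 380 |
|---|---|---|
| None | 0 | 0 |
| One third | 12.7 (about 13) | 3.3 |
| One half | 19 | 5.0 |
| All | 38 | 10.0 |

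**6. How far could they move the TRC3 estimate?** Assume 85.5 women per arm with all three cycles, *k* women per arm with TRC1 only, and a correlation ρ between cycles. If the TRC1-only women differ by 1 point at TRC1, the arm's TRC3 mean shifts by about ρ × *k*/(85.5 + *k*).

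- *k* = 3.17 (one third of dropouts), ρ = 0.3: 0.3 × 3.17/88.67 = 0.01.
- *k* = 9.5 (all dropouts), ρ = 0.8: 0.8 × 9.5/95 = 0.08.

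The range is 0.01 to 0.08 points, against a design difference of 1 point. Equal shifts in two arms cancel in the comparison.

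**7. What do other planned runs cover?** One SAP 8.3.6 sensitivity analysis drops cycles with fewer than 10 NMPP or fewer than 2 DYS scores, so a retained cycle has at least 12 scored days. Days after the last dose do not count towards TRC1–TRC3 (SAP 8.3.3.1). A woman stopping before day 12 of TRC1 thus contributes nothing to that run; one who stops later in TRC1 can remain.

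**The case against.** The strongest reply is that other planned runs already examine dependence on early stoppers. The diary-count analysis removes the earliest ones. The observed-TRC3 ANCOVA leaves out everyone who stopped in TRC1 or TRC2, and comparing it with the LOCF ANCOVA shows what women without TRC3 data contribute. This largely stands. What remains is that the diary-count run targets missing diary data and is not applied to the PP set. The observed-TRC3 ANCOVA also still includes women who stopped during TRC3, since one score suffices, and the protocol lists the ANCOVA and the completers analysis separately.

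Second, a reader might infer that women who stop within days always count as per-protocol. The documents do not show that. Some may be removed as critical or major deviations, which are classified under a deviation plan that is not among the documents. However, protocol 7.2 lists intolerable adverse events and withdrawn consent as justifiable reasons to stop, so stopping is not in itself clearly a deviation.

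Third, a reader might infer that the SAP's PP run merely repeats the MFAS analysis and cannot reveal dependence on stoppers because the condition was dropped. That goes too far. The protocol's own PP set also keeps women who stop in TRC2 or TRC3, and the SAP's exclusions still remove some women.

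Finally, protocol 9.4.1 calls its section a summary and leaves analysis sets and methods to the SAP. The SAP may therefore refine them, but that does not make the statement in SAP 10 accurate.

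**Conclusion.** The mismatch is established by the text. The PP set lacks the protocol's one-cycle condition, the 75% rule cannot stand in for it, and the PP ANCOVA and the completers analysis are missing. SAP 10 is wrong as written.

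The consequence is modest. The primary MFAS MMRM, the sample size and the power are untouched, and nothing here puts the primary result in doubt. About 13 to 19 women (3–5%) would be in the SAP's PP set but not the protocol's. That count assumes 10% dropout, a third to a half of stops in TRC1, and no removal of these women through the deviation criterion. The shift in the TRC3 estimate is small under the correlations tried. The loss lies in what the PP and completers results can be said to show, and in a departure that is not disclosed. This should be corrected, but it is not critical.

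**What to change.** Before unblinding:

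- In SAP 6.5, restore the requirement of at least one completed treatment cycle and state how completion of a cycle is determined from the data.
- In SAP 8.3.6 or 8.3.7, add the ANCOVA on the PP set and an analysis of women who completed all three cycles. Completion of treatment is already recorded on the End of Study Treatment eCRF page (SAP 8.2.1).
- In SAP 10, replace the no-change statement with a list of every departure, including the new 75% compliance criterion, and give the reason for any that is kept on purpose.

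The cost is SAP wording, two or three extra model runs on existing data, and a slightly smaller PP set. The completers result should be labelled supportive only, because it selects women on completion after randomisation and does not target the primary estimand.
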